7. STATISTICAL METHODS AND DETERMINATION OF SAMPLE SIZE

7.1 STATISTICAL DESIGN – MODEL

This trial will be performed as an open-label single-arm study. The primary objective of the trial is to determine the RP2D of BI 836826 in combination with ibrutinib. The RP2D will be either the MTD or a lower dose. To determine the MTD, patients are entered sequentially into escalating dose cohorts. The dose-finding will be guided by a Bayesian 5-parameter logistic regression model with overdose control ([R13-4806](#)), ([R13-4803](#)). This design is based on practical experience and is a preferable algorithmic method due to its superior ability to identify the dose with a desired toxicity rate and its allocation of a greater proportion of patients to doses at, or close to, that dose ([R13-4802](#), [R13-4804](#), [R13-4805](#)).

In the following, DLT denotes a dose-limiting toxicity occurring during the first cycle. The 5-parameter logistic regression model is defined as follows. Let $\pi_{1,d1}$ be the probability of having a DLT when giving dose d_1 of BI 836826, and $\pi_{2,d2}$ the probability of having a DLT when giving dose d_2 of ibrutinib, respectively. A logistic regression is used to model the dose-toxicity relationship for each of these drugs individually:

$$\begin{array}{ll} \text{BI 836826:} & \text{logit}(\pi_{1,d1}) = \log(\alpha_1) + \beta_1 \log(d_1/d_1^*) \\ \text{Ibrutinib:} & \text{logit}(\pi_{2,d2}) = \log(\alpha_2) + \beta_2 \log(d_2/d_2^*) \end{array}$$

Here, the doses $d_1^* = 200\text{mg}$ and $d_2^* = 420\text{mg}$ BBB represent the reference doses for BI 836826 and ibrutinib, respectively.

Under independence, the probability of a DLT when giving the combination dose d_1, d_2 is obtained as

$$\pi_{12,d1,d2}^0 = \pi_{1,d1} + \pi_{2,d2} - \pi_{1,d1}\pi_{2,d2}$$

with corresponding odds

$$\text{odds}(\pi_{12,d1,d2}^0) = \pi_{12,d1,d2}^0 / (1 - \pi_{12,d1,d2}^0)$$

In order to account for a potential positive (higher toxicity than expected under independence) or negative (lower toxicity than expected under independence) interaction between BI 836826 and ibrutinib, a dose-dependent interaction term $-\infty < \eta < \infty$ is introduced in the model:

$$\text{odds}(\pi_{12,d1,d2}) = \text{odds}(\pi_{12,d1,d2}^0) \exp(\eta \log(d_1/d_1^*) \log(d_2/d_2^*))$$

and $\pi_{12,d1,d2}$ is used in the likelihood

$$r_{d1,d2} \sim \text{Binomial}(n_{d1,d2}, \pi_{12,d1,d2})$$

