where $r_{d1,d2}$ denotes the number of DLTs observed in $n_{d1,d2}$ patients at dose combination d_1, d_2 . Since a Bayesian approach is applied, prior distributions f for each of the parameter vectors $\theta_1 = (\log(\alpha_1), \log(\beta_1))$, $\theta_2 = (\log(\alpha_2), \log(\beta_2))$ and for the interaction term η need to be specified.

The prior distributions for θ_k will be specified as a mixture of two bivariate normal distributions,

$$f(\theta_k) = a_{1,k} f_1(\theta_k) + a_{2,k} f_2(\theta_k)$$

with

$a_{1,k}, a_{2,k}$ the prior mixture weights ($a_{1,k} + a_{2,k} = 1$), $k=1,2$ and

$f_i(\theta_k) = \text{MVN}(\mu_{ik}, \Sigma_{ik})$ a bivariate normal distribution with mean vector μ_{ik} and covariance matrix Σ_{ik} where

$$\Sigma_{ik} = \begin{pmatrix} \sigma_{ik,11}^2 & \sigma_{ik,11}\sigma_{ik,22}\rho_{ik} \\ \sigma_{ik,11}\sigma_{ik,22}\rho_{ik} & \sigma_{ik,22}^2 \end{pmatrix}$$

Mixture prior distributions have the advantage that they allow for specification of different logistic dose-toxicity curves, therefore making the prior more robust. A weakly-informative normal prior distribution will be used for η .

The estimated probability of DLT at each dose level from the model will be summarized using the following intervals:

Under dosing: [0.00, 0.16)

Targeted toxicity: [0.16, 0.33)

Over dosing: [0.33, 1.00]

The BLRM-recommended dose for the next cohort is the level at which the probability for the target toxicity interval is maximal out of the dose candidates satisfying the escalation overdose control criterion EWOC. Per EWOC it should be unlikely (<25% posterior probability) that the DLT rate at the dose combination will exceed 0.33. The overdose control criterion requires the probability of overdosing to be below 0.25. However, the maximum allowable dose increment for the subsequent cohort will be no more than 100% for each drug

The MTD may be considered reached if the following criteria are fulfilled:

1. The posterior probability of the true DLT rate in the target interval [0.16 – 0.33) of the MTD is above 0.50, OR
2. At least 15 patients have been treated in the study, of which at least 6 at the MTD.

Prior derivation:

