10.7 STATISTICAL APPENDIX INCLUDING MODEL PERFORMANCE AND DATA SCENARIOS

The model was assessed by two different metrics: hypothetical on-study scenarios and long-run operational characteristics.

Hypothetical Data Scenarios

Hypothetical data scenarios are shown in [Table 10.7:1](#). These scenarios reflect the potential on-study data constellations and related escalation as allowed by the model and the 100% escalation limit. For each scenario, the probability of overdose for the current dose, as well as the next potential dose and related probabilities of under-dosing, target toxicity and over-dosing are shown.

For example, scenario 1 represents the case that no DLT is observed in three patients at the starting dose of 420mg on Ibrutinib and 100mg of BI 836826. In this case, the next dose permitted by the model and by the 100% escalation rule is 420mg of Ibrutinib and 200mg of BI 836826. Similarly, scenario 6 represents the case that no DLT is observed in the first cohort of 3 patients at 420mg of Ibrutinib and 100mg of BI 836826, and 1 DLT is observed in the cohort of 3 patients at 420mg Ibrutinib and 200 mg of BI 836826. In this case, the model suggests re-enrolling patients at the current dose level of 200mg BI 836826.

In scenario 17, 1 DLT is observed with 6 patients at a BI 836826 dose of 200mg. Here, the model suggests to only increase the dose up to 300mg BI 836826 and to not use the 100% dose escalation. In scenario 22, it is assumed that at a dose of 1400mg BI 836826, 2 DLTs occur in 3 patients. Despite the fact that no DLTs have been observed in the previous 4 cohorts, the model reacts immediately to the data observed and requires de-escalation to 600mg. This case illustrates the adaptive behavior of the model in more extreme situations.

Table 10.7:1 Hypothetical data scenarios

Scenario	Dose Ibrutinib, BI 836826 [mg]	# DLT	# Pat	Current dose:	Next dose Ibrutinib, BI 836826 [mg]	Next dose		
				P(over dosing)		P(under dosing)	P(target toxicity)	P(over dosing)
1	420,100	0	3	0.036	420, 200	0.577	0.304	0.119
2	420,100	1	3	0.201	420, 100	0.431	0.394	0.174
3	420,100	2	3	0.491	NA	NA	NA	NA
4	420,100	0	2	0.055	420,200	0.541	0.316	0.144
5	420, 100	0	3	0.033	420, 400	0.498	0.254	0.248
	420, 200	0	3					
6	420, 100	0	3	0.208	420, 200	0.418	0.418	0.163
	420, 200	1	3					
7	420, 100	0	3	0.426	420, 100	0.429	0.43	0.141
	420, 200	2	3					
8	420, 100	1	3	0.227	420, 100	0.304	0.47	0.227
	420, 100	1	3					
9	420, 100	1	3	0.063	420, 200	0.399	0.401	0.2

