		longer required as per the amendment.
Section to be changed		Section 5.3.7
Description of change		
Schematic representation of study deleted.
 
Deleted sentences- “BI 836826 related events which occurred after the REP will be considered as post treatment events. Events attributed to ibrutinib only or not-related events will not be reported after the REP.”
 
Modified paragraph on Information required to read as “For each AE, the Investigator should provide the information requested on the appropriate (e)CRF pages and the BI SAE form (if applicable)” and deleted the remainder of the paragraph.
 
Paragraph on exemptions to SAE reporting: However, when there is evidence suggesting a causal relationship between the study drug and the progression of the underlying malignancy, the event must be reported as an (S)AE on the SAE form and on the (e)CRF.

Rationale for change		Since there is no extended follow up period after the REP, section has been updated. Section on “AE collection”, “Information required” and “exemptions to SAE reporting” has been updated to reflect current BI reporting practices.
Section to be changed		
Section to be changed		Section 5.5.1.1
Description of change		
Rationale for change		Deleted to mirror the flow chart.
Section to be changed		Section 5.5.2 modified and 5.5.3 deleted
Description of change		

Rationale for change		
Section to be changed		Section 6.2.3 and 6.2.3.2
Description of change		Trial completion for an individual patient has been clarified.
Rationale for change		Extended Follow up period has been removed. Section clarified to indicate criteria for trial completion.
Section to be changed		Section 7.3
Description of change		Removal of the sub-group analysis
Rationale for change		Since the trial is being stopped prior to reaching the MTD, the subgroup analysis will not be performed.
Section to be changed		Section 7.4
Description of change		Sentence deleted- “In addition, after determination of the RP2D in the Phase Ib part of this trial, a synoptic interim report will be written to justify the RP2D”.
Rationale for change		Since Phase II of the trial will not be conducted, an interim report will not be prepared.
Section to be changed		Section 8.4.2
Description of change		Expedited Reporting of Adverse Events section updated.
Rationale for change		Section updated to reflect current BI reporting requirements.
Section to be changed		Section 8.6

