#### **5.2.2 Other secondary endpoints**

The secondary endpoint is the MTD. The MTD may be considered reached if the posterior probability that the true DLT rate is in the target interval  $[0.16, 0.33)$  is larger than 0.5 or if at least 15 patients have been treated in the Phase Ib part, of which at least 6 at the MTD. Patients who have been replaced are not considered evaluable for MTD determination. Only DLTs occurring in the MTD evaluation period will be considered for the determination of the MTD

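### The MTD rule joins its two criteria by OR: the first has no patient minimum, and neither makes the 0.25 overdose limit a written condition for the declared MTD

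*Protocol*

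**What the plan says.** Protocol 7.1 gives two conditions under which the MTD may be considered reached. The first is that the posterior probability of the target interval [0.16, 0.33) "of the MTD is above 0.50, OR" the second: "At least 15 patients have been treated in the study, of which at least 6 at the MTD". SAP 5.2.2 keeps the same structure: the posterior probability "is larger than 0.5 or if at least 15 patients have been treated in the Phase Ib part", with at least 6 at the MTD. SAP 5.2.2 also says: "Patients who have been replaced are not considered evaluable for MTD determination".

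The overdose limit appears earlier in Protocol 7.1: "The overdose control criterion requires the probability of overdosing to be below 0.25". There it restricts the dose for the next cohort. Protocol 3.1 applies it to escalation. More generally, Protocol 7.1 describes dose finding as "guided by a Bayesian 5-parameter logistic regression model with overdose control", and SAP 7.4 says that the EWOC principle guides the MTD analysis.

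Other safeguards lie outside the rule. Protocol 3.1 requires at least 6 patients at the RP2D and allows, but does not require, extra patients to confirm the MTD. Protocol 4.1.4 requires consensus before an MTD is declared.

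**The concern.** The MTD is the secondary endpoint, and this rule is its written definition. Because of the OR, the 6-patient minimum protects only the second route. The first route depends on the model alone, which can put more than half of its probability in the target interval at a dose it reached by interpolation. The second route depends on head counts alone and holds whatever the DLT data show. Neither asks whether the dose still meets the overdose limit. The report could therefore name an MTD with little or no direct data behind it, or one to which the protocol would not assign another cohort. The MTD also caps the RP2D, which is the MTD or a lower dose.

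**Working it through.** **Inputs.** Priors from Protocol Table 7.1:3. DLT data from Table 10.7:1, plus one constructed path. Target [0.16, 0.33), overdosing from 0.33, limit 0.25.

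**Model.** Each drug has logit(π) = log(α) + β·log(d/d*), with d* = 200 mg for BI 836826 and 420 mg for ibrutinib. Under independence π⁰ = π₁ + π₂ − π₁π₂, and the odds are then multiplied by an interaction term. In the form printed in Protocol 7.1 that term is exp(η·log(d₁/200)·log(d₂/420)). It equals 1 at 420 mg ibrutinib, because log(420/420) = 0. The form exp(η·(d₁/200)·(d₂/420)) reproduces the protocol's tables better and is called the tabulated form here. Results are given for both. The posterior was obtained by weighting 3,000,000 prior draws by the binomial likelihood.

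**Reproducing the plan's figures** (tabulated form; under / target / over):

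| Case | Recomputed | Protocol |
|---|---|---|
| Prior, 200 mg | 0.445 / 0.313 / 0.242 | 0.448 / 0.312 / 0.241 |
| Scenario 18, 200 mg | 0.298 / 0.505 / 0.198 | 0.291 / 0.503 / 0.206 |
| Scenario 20, 400 mg | 0.253 / 0.548 / 0.199 | 0.258 / 0.541 / 0.201 |
| Scenario 22, 600 mg | 0.318 / 0.557 / 0.125 | 0.321 / 0.552 / 0.127 |

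Agreement is within about 0.01.

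**Criterion 1 and patient numbers.**
- Scenario 20 has 0/3 at each of 100, 200 and 400 mg and 2/3 at 800 mg. The next dose is 400 mg, where 3 patients were treated: 0.541 > 0.50.
- Scenario 22 has 0/3 at each of 100, 200, 400 and 800 mg and 2/3 at 1400 mg. The appendix says "the model reacts immediately to the data observed and requires de-escalation to 600mg". Nobody was treated at 600 mg: 0.552 > 0.50.

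Both values satisfy criterion 1 as written.

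**Criterion 2 and the overdose limit.** Start with 0/3 at 100 mg and follow 200 mg in cohorts of 3:

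| DLTs at 200 mg | P(over), tabulated form | P(over), printed form | Within limit? |
|---|---|---|---|
| 1/3 (scenario 6) | 0.162 (next-dose row: 0.163) | 0.126 | yes |
| 2/6 (scenario 18) | 0.198 (table: 0.206) | 0.155 | yes |
| 3/9 | 0.226 | 0.180 | yes |
| 5/12 | 0.443 | 0.374 | no |

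At the last row, 3 + 12 = 15 patients have been treated, 12 of them at 200 mg, so criterion 2 is met at 200 mg while the overdose probability is well above 0.25. P(target) there is 0.502 (tabulated) or 0.559 (printed). Criterion 1 is therefore also met, but only marginally in the tabulated form. With the same data, 100 mg has 3 patients and P(target) 0.525 or 0.534, so criterion 1 would also admit 100 mg on 3 patients.

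**How often the patient gap would matter.** Two indicative simulations used cohorts of 3 (assumed), the doses and true DLT rates of Table 10.7:2, and the next recommended dose as the declared MTD. An MTD rested on fewer than 6 patients in 1.85/1.70/1.35/1.80% of trials (scenarios 1 to 4, 2000 trials each) in one, and in 1.5/2.6/2.5/1.7% (1000 each) in the other. It rested on no patients in 0% in both. Mean sample sizes in the first run were 13.63/10.66/15.28/15.19, against 16.10/11.58/19.47/18.66 in Table 10.7:3. The table is thus not reproduced and the rates are only a guide. Its cohort-size and stopping assumptions are not stated, so this does not show that the table is wrong.

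**The case against.** The best defence is that the criteria are stopping conditions for a dose already chosen. Both speak of the MTD as if it were identified, and they follow directly after the rule that picks the dose with the highest target probability among those meeting EWOC. On that reading the overdose limit has already filtered the candidates. The appendix behaves this way: scenario 19 (3/6 at 200 mg, overdose probability 0.44) moves down to 100 mg, and 5/12 would do so too. This is probably what was meant. But neither document makes the limit a condition for the dose finally reported, and a reference to a guiding principle is not a numeric criterion.

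The practical defences stand. The rule is permissive, consensus is needed, and an MTD on fewer than 6 patients could not become the RP2D without more data. These reduce the consequence but do not complete the definition.

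Three stronger inferences are not supported:
- A reader might infer that the protocol declares an MTD at an untreated dose in scenario 22. It does not; the row gives the next dose.
- A reader might infer that MTDs failing the limit would be frequent. No frequency is available: the simulations impose EWOC on the declared dose, so they do not test that gap.
- A reader might offer 4/12 at 100 mg (target 0.576, over 0.270, tabulated form) as a further example. It does not hold up. When 100 mg fails the limit, Table 10.7:1 shows no next dose and the appendix counts the trial as stopped for toxicity. The preceding step, 3/9 at 100 mg, gives an overdose probability of 0.247. That is too close to 0.25, given that scenario 8 (2/6 at 100 mg) recomputes to 0.218 against a printed 0.227.

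**Conclusion.** The point holds as a gap in the written definition of the secondary endpoint, and it is minor. Criterion 1 can be met on 3 patients or none, as the protocol's own table shows. Criterion 2 can be met at a dose whose overdose probability is about 0.37 to 0.44 against a limit of 0.25.

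The table-based part rests only on printed figures. The 200 mg example rests on the Table 7.1:3 priors, cohorts of 3, and either form of the interaction. The excess over 0.25 is far larger than the reproduction error of about 0.01.

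The effect on this trial is likely to be small. Under the reading in which EWOC filters the declared dose, an MTD on fewer than 6 patients arises in about 1 to 3% of simulated trials. The rationale for the Section 7.3 change in Protocol Section 11 reads "Since the trial is being stopped prior to reaching the MTD". That is the reason to tidy the rule: the SAP, finalised after the amendment, still contains a definition under which the report could name an MTD. The finding does not show that any patient was or would be assigned to a dose outside the limit, because the limit does govern escalation and the next-cohort dose.

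**What to change.** Changing SAP 5.2.2 is sufficient. Suggested content: a dose is reported as the MTD only if, at the final analysis, its posterior probability of overdosing is below 0.25 and at least 6 MTD-evaluable patients were treated at it, and, in addition, either its posterior target probability exceeds 0.50 or at least 15 patients have been treated. If no dose qualifies, no MTD is reported and only the posterior probabilities already planned in SAP 7.4 are shown.

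The figure of 6 is already in criterion 2 and is already required for the RP2D. Counting MTD-evaluable patients follows the SAP's exclusion of replaced patients, and the count of 15 is unchanged. Applying the minimum of 6 to the first route is stricter than the present text, not merely a clarification. In the 1000-trial simulation this changed the share of trials declaring a dose in the target range by at most 0.2 percentage points (76.3 to 76.2%, 67.6 to 67.7%, 32.7 to 32.9%, 26.6 to 26.6%).

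The cost is two sentences, with no new data or analysis. The downside is that possibly no MTD is reported, as in the 200 mg example, where neither 200 mg nor 100 mg would qualify at that point. The amendment already anticipates that outcome.

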3. DESCRIPTION OF DESIGN AND TRIAL POPULATION

3.1 OVERALL TRIAL DESIGN AND PLAN

This is a single arm, open label, phase Ib dose escalation study. Approximately 20 relapsed/refractory CLL patients who have been pre-treated with at least one prior line of systemic treatment and who qualify for treatment with ibrutinib will be treated with a combination of BI 836826 and ibrutinib in this trial.

Ibrutinib is to be dosed at a fixed, approved dose of 420mg daily in all patients. Stepwise dose escalation of BI 836826 will be performed. BI 836826 will be administered on cycle 1 on following days: D1 (10mg), D2 and D8 (50% of the assigned dose on each day), D15 (100% dose). In C2-4 BI 836826 will be administered on days: 1 and 15 of each cycle at 100% of the assigned dose.

Dose-escalation of BI 836826 will be guided by a BLRM with overdose control (refer to [Section 7](#)). The BLRM estimates the MTD by updating estimates of the probability of observing a DLT in the first cycle for each dose level in the study as patient information becomes available. At any time in the trial, it will not be permitted to escalate to a dose which does not fulfil the Escalation With Overdose Control (EWOC) criterion (refer to Section 7). Dose-increments will be $\leq 100\%$ of the previous dose level tested in prior cohort.

For any dose-escalation cohort, at least 3 patients will be required (Section 7). However, in the case that only 2 patients are evaluable and neither has experienced a dose-limiting toxicity within the first cycle (28 days) of the combination treatment, then dose-escalation can occur based on these 2 patients.

A patient will be considered evaluable for DLT in cycle 1 (D1 to D28 of combination treatment)

- if the patient has been observed for at least one cycle and has had sufficient exposure to both study drugs, i.e. 4 infusions of BI 836826 (10 mg, 50% of target dose x 2, and 100% of target dose x1) and $\geq 80\%$ (22 of 28 doses) of ibrutinib doses.
- if the patient has experienced a DLT independent of exposure time in cycle 1.

Patients who do not meet at least one of the above criteria will be considered for the safety analysis, but will be replaced by an additional patient for DLT assessment.

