To determine the prior distributions for $(\log(\alpha_1), \log(\beta_1))$ and $(\log(\alpha_2), \log(\beta_2))$, a meta-analytic predictive (MAP) approach will be used. Toxicity information on BI 836826 from the 1270.1 Phase I study and from two published studies of ibrutinib will be incorporated. Exact details on the derivation of the prior distributions and on the evaluation of the model using hypothetical data scenarios and operating characteristics are provided in the statistical appendix; a brief description is given here.

The historical data for BI 836826 can be found in [Table 7.1:1](#). For ibrutinib, the historical data can be found in [Table 7.1:2](#).

Table 7.1:1 Historical data for BI 836826

Study	Dose(mg)	N of DLTs during first cycle / N of patients
1270.1		
	1	0/3
	3	0/3
	9	0/6
	25	0/6
	50	0/3
	100	0/3
	200	1/6
	400	0/3
	800	1/2

Table 7.1:2 Historical data for ibrutinib

Study	Dose(mg)	N of DLTs / N of patients
Byrd et al*		
	420	2 / 51
	840	4 / 34
Advani et al**		
	87.5	0 / 7
	175	1 / 9
	350	0 / 6
	560	0 / 9
	581	1 / 18
	875	0 / 7

* No DLTs were reported for this study. The number of DLTs was therefore approximated by the number of AEs leading to discontinuation.

** Dosing based on mg/kg was used. The corresponding fixed dose was calculated as the dose corresponding to a weight of 70kg.

The following steps were used to derive the prior distributions for all parameters:

1. $\log(\alpha_1)$, $\log(\beta_1)$:
 - a. The meta-analytic-predictive prior was derived using the information in [Table 7.1:1](#), allowing for moderate to substantial between-trial heterogeneity. This mixture component was assigned 90% mixture weight.
 - b. A second, weakly-informative component was added with 10% mixture weight.
2. $\log(\alpha_2)$, $\log(\beta_2)$:
 - a. The meta-analytic-predictive prior was derived using the information in [Table 7.1:2](#), allowing for large to very-large between-trial heterogeneity. This mixture component was assigned 90% mixture weight.
 - b. A second, weakly-informative component was added with 10% mixture weight.
3. η : based on the a priori assumption of no interaction between the two compounds, a normal distribution with mean 0 and standard deviation 0.56 was chosen. At the starting dose combination, the corresponding 95% prior interval covers an up to 1.4 fold increase (or decrease) in the odds of DLT over no interaction.

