The prior distributions are given in [Table 7.1:3](#). The corresponding prior probabilities of a DLT at different doses and the corresponding probability of under-dosing, targeted dosing and overdosing are shown in [Table 7.1:4](#). As can be seen from [Table 7.1:4](#), the dose combination 100mg BI 836826 and 420mg ibrutinib has prior probability of overdosing below 25%; it fulfills the overdose criterion and is therefore a suitable starting dose combination.

Table 7.1:3 Prior distributions

Parameter	means, standard deviations, correlation	mixture weight
$\log(\alpha_1), \log(\beta_1)$: component 1	(-2.282, 0.062, 1.065, 0.699, -0.105)	0.9
$\log(\alpha_1), \log(\beta_1)$: component 2	(-2.282, 0.062, 2, 1, 0)	0.1
$\log(\alpha_2), \log(\beta_2)$: component 1	(-2.819, -0.522, 1.303, 0.926, -0.047)	0.9
$\log(\alpha_2), \log(\beta_2)$: component 2	(-2.819, -0.522, 2, 1, 0)	0.1
η	0, 0.56	N/A

Table 7.1:4 Prior probabilities of DLT

Dose BI 836826	Dose ibrutinib	Probability of true DLT rate in			Mea n	StD	Quantiles		
		[0,0.16]	[0.16,0.33]	[0.33,1]			2.5%	50%	97.5%
50mg	420mg	0.695	0.209	0.096	0.144	0.140	0.011	0.099	0.545
100mg	420mg	0.607	0.262	0.131	0.171	0.150	0.016	0.125	0.592
200mg	420mg	0.448	0.312	0.241	0.233	0.181	0.025	0.181	0.707
300mg	420mg	0.347	0.279	0.373	0.302	0.226	0.025	0.243	0.843
400mg	420mg	0.305	0.232	0.463	0.361	0.268	0.021	0.298	0.931

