## **7.4 PRIMARY ENDPOINTS**

The primary endpoints are the RP2D and the number of patients with DLTs in the MTD evaluation period. The number of patients with DLTs at each dose level will be presented for the MTD evaluation period for the MTD evaluation set and for the whole on-treatment period for the treated set separately.

The RP2D will either be the MTD or any lower dose, examined based on safety and efficacy criteria. The analysis of the MTD is based on a BLRM guided by the EWOC principle. Estimation of the MTD during the dose escalation phase of the study will be based upon the estimation of the posterior probability of the incidence of DLT in toxicity categories during the MTD evaluation period for all evaluable patients. The model to be used is specified in CTP Section 7.

The posterior probabilities that the toxicity rates of each dose level fall into the categories specified in CTP Section 7 estimated from the BLRM will be displayed graphically as well as in a table. This will be done for the MTD evaluation period as well as for the complete on-treatment period.

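### The printed BLRM interaction factor equals 1 at every dose, the protocol's tables follow a different form, and the 1.4-fold prior range fits neither

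*Protocol*

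**What the plan says.** Protocol Section 7.1 describes a "Bayesian 5-parameter logistic regression model with overdose control". Each drug has its own logistic dose-toxicity curve. The two are combined under independence, and the resulting odds are multiplied by `exp(eta*log(d1/d1*)*log(d2/d2*))`. The term is there to allow toxicity above or below independence; the text introducing it reads, in part, "interaction between BI 836826 and ibrutinib, a dose-dependent interaction term". The doses `d1*` = 200 mg and `d2*` = 420 mg "represent the reference doses for BI 836826 and ibrutinib, respectively".

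Protocol Section 3.1 states: "Ibrutinib is to be dosed at a fixed, approved dose of 420mg daily in all patients".

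Step 3 of the prior derivation in Section 7.1 gives `eta` a normal prior with mean 0 and SD 0.56. It adds that, at the starting combination (100 mg with 420 mg), the 95% prior interval "covers an up to 1.4 fold increase (or decrease) in the odds of DLT over no interaction".

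Table 7.1:4 gives the prior DLT probabilities that follow from these priors. Table 10.7:1 in Section 10.7 gives posterior probabilities for hypothetical datasets, of which the protocol says: "These scenarios reflect the potential on-study data constellations and related escalation as allowed by the model and the 100% escalation limit".

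For the final analysis, SAP Section 7.4 says: "The model to be used is specified in CTP Section 7". It asks for the posterior interval probabilities at each dose level in a table and a graph.

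**The concern.** With ibrutinib at its own reference dose, the second logarithm in the printed term is `log(420/420)` = 0. The term meant to capture interaction then does nothing, and `eta` drops out of the likelihood. As printed, only three of the five parameters are active: `log(alpha1)`, `log(beta1)` and `log(alpha2)`. (`log(beta2)` drops out under any interaction form, because `d2` = `d2*` in the ibrutinib curve.) This contradicts the stated purpose of the term and leaves the 1.4-fold sentence without a meaning.

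The SAP points to this section and gives no other formula in its visible text. An analyst who codes the model as printed would produce RP2D and MTD posteriors without an interaction, and these would not agree with the protocol's escalation tables. It would also be unclear which model stood behind the decisions of the Safety Review Committee (SRC).

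**Working it through.** **Inputs.** Interaction formula, reference doses, `eta` ~ N(0, SD 0.56) and the mixture priors of Table 7.1:3 (protocol Section 7.1); ibrutinib 420 mg throughout (Section 3.1); starting dose 100 mg (Section 4.1.3); overdose limit 0.25 (Section 7.1).

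**1. The 1.4-fold figure.** The upper 95% limit of the odds multiplier is `exp(1.96 × 0.56 × g)`, where `g` is the dose term.
- As printed: `g = log(0.5) × log(1) = 0`, so the limit is 1.00.
- Plain ratios: `g = 0.5 × 1 = 0.5`, so the limit is `exp(0.549)` = 1.73.
- For 1.4 with plain ratios, the SD would have to be `ln(1.4)/(1.96 × 0.5)` = 0.343. With SD 0.56, the range 1/1.4 to 1.4 holds only 77% of the prior.
- Other readings under plain ratios also miss 1.4: a 90% interval gives 1.58, an 80% interval 1.43, 0.56 read as a variance 2.08, and 0.56 squared used as the SD 1.36. A reference dose near 326 mg would give 1.4, but the protocol states 200 mg.

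**2. A check that needs no simulation.** `beta1` is the exponential of `log(beta1)` and so is positive. With the factor equal to 1, every prior draw's DLT rate rises with the BI 836826 dose, and no quantile can fall. Table 7.1:4 shows the 2.5% quantile falling from 0.025 at 300 mg to 0.021 at 400 mg. The printed formula cannot give that.

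**3. Table 7.1:4 recomputed.** 3 million draws from the Table 7.1:3 priors; P(under)/P(target)/P(over):

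| BI 836826 | Protocol table | As printed | Plain ratios |
|---|---|---|---|
| 200 mg | 0.448/0.312/0.241 | 0.438/0.353/0.208 | 0.444/0.314/0.242 |
| 300 mg | 0.347/0.279/0.373 | 0.301/0.368/0.331 | 0.344/0.282/0.374 |
| 400 mg | 0.305/0.232/0.463 | 0.227/0.340/0.433 | 0.302/0.234/0.464 |

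At 400 mg the 2.5% quantile is 0.021 in the table, 0.021 with plain ratios and about 0.055 as printed. The largest gap in the table's interval probabilities is 0.108 as printed and 0.006 with plain ratios. At 100 mg, P(over) is 0.125 as printed against 0.131 tabulated, so the starting dose meets the overdose criterion either way.

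**4. Table 10.7:1 recomputed.** The same draws weighted by the binomial likelihood (effective sample size at least 0.41 million, Monte Carlo error below 0.001):

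| Scenario and dose | Quantity | Protocol table | As printed | Plain ratios |
|---|---|---|---|---|
| 13, next 800 mg | under/target/over | 0.622/0.168/0.209 | 0.346/0.364/0.290 | 0.632/0.160/0.208 |
| 21, next 1400 mg | under/target/over | 0.833/0.083/0.084 | 0.388/0.373/0.239 | 0.838/0.081/0.082 |
| 6, next 200 mg | over | 0.163 | 0.125 | 0.162 |
| 18, next 200 mg | over | 0.206 | 0.155 | 0.198 |
| 20, next 400 mg | over | 0.201 | 0.165 | 0.199 |
| 14, current 400 mg | over | 0.284 | 0.244 | 0.287 |

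Over the 18 distinct datasets with a next dose, the largest gap is 0.445 as printed (scenario 21, P(under) 0.388 against 0.833) and 0.010 with plain ratios. Scenario 13 clearly changes status: 800 mg passes the 0.25 limit in the table and fails it as printed. Scenarios 14 (above) and 15 (0.252 as printed against 0.218 tabulated) also cross the limit, but their printed-form values lie within 0.006 of it.

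**5. What `eta` learns.** As printed, its posterior stays at the prior (mean 0.00, SD 0.56). With plain ratios it moves to -0.35 (SD 0.50) in scenario 13 and -0.54 (SD 0.43) in scenario 21.

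The simulated operating characteristics in Table 10.7:3 were not re-run.

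**The case against.** The strongest reply is that the formula may be misread rather than wrong. The equation was machine-read from PDF and sits below two lines that do contain `log(d/d*)`. The tables themselves show that a working interaction term was programmed, so the final analysis would probably reuse that program. This stands as a caveat: the formula should be checked against the original PDF. It does not rescue the 1.4-fold sentence, which is wrong under plain ratios too. That sentence feeds no calculation, however; SD 0.56 is printed twice and the tables agree with it.

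Plain ratios also do not match every cell. In the current-dose column, scenario 6 shows 0.208 where plain ratios give 0.162, and scenario 2 shows 0.201 where they give 0.180. Both cells disagree with the table's own next-dose values for the same dose and data (0.163 and 0.174), and the printed form is further off (0.125 and 0.169). They look like table errors and do not support the printed form.

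The headings for clarifications and changes in SAP Section 4 have no visible text beneath them. If text was removed there, it could contain a correction.

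Finally, development has stopped, recruitment is closed, the analyses are descriptive and an abbreviated report is planned. The changes in overdose status occur in hypothetical datasets. This limits the consequence but does not remove it, because SAP Section 7.4 still requires the BLRM posteriors for the primary endpoint.

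**Conclusion.** The concern holds. As printed, the interaction factor is exactly 1 for every planned dose combination. Tables 7.1:4 and 10.7:1 agree with plain dose ratios and SD 0.56, apart from the two inconsistent current-dose cells. The stated 1.4-fold range is 1.00-fold under one form and 1.73-fold under the other.

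Coding the printed form would not err in one direction. P(over) is lower than tabulated in scenarios 6, 14, 18 and 20, and higher in scenarios 13, 15 and 21, so it cannot be dismissed as conservative.

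The conclusion rests on the Table 7.1:3 priors as printed and on ibrutinib entering the model at 420 mg, as it does in every row of both tables. That plain ratios were programmed is an inference from the match; the documents do not show the software. What remains live is the SAP Section 7.4 output and whether past SRC decisions can be traced to a stated model. It should be fixed.

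**What to change.** 1. Check the BLRM program used for the SRC and state its interaction form in protocol Section 7.1, with SAP Section 7.4 referring to it. If it was plain ratios: `odds(pi12) = odds(pi0_12) × exp(eta*(d1/d1*)*(d2/d2*))`.
2. Replace the 1.4-fold statement and give the 95% prior odds range at each planned tier. With plain ratios and SD 0.56, `exp(1.96 × 0.56 × d1/200)` gives about 1.7, 3.0, 9.0, 27, 81 and 2,170-fold at 100, 200, 400, 600, 800 and 1400 mg.
3. Produce the SAP Section 7.4 posterior table and graph from that same stated model, so that formula, prior statement, tables and final analysis agree.

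The cost is one program check and two wording corrections, with no new simulations or patients. A formal change to protocol Section 7.1 would need the approvals that Section 8.1 attaches to amendments; a clarification in the SAP would serve the same purpose without that step. The text would then show openly how wide the prior interaction range is at the upper tiers.
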